IRB# 5120263 A phase II study of preoperative proton therapy in soft tissue sarcomas of the extremities and body wall

NCT# 01819831

Principal Investigator

[name]

Co-Investigators (in alphabetical order)

[name]

[name], PhD

[name] , MD, PhD

[name], PhD

[name]

[name]

[name]

[name]

LLUH IRB approval: 10/3/2012

[figure not shown]
Index

Schema

- 1.0 Introduction**
- 2.0 Objectives**
- 3.0 Patient Selection**
- 4.0 Drug Therapy**
- 5.0 Surgery**
- 6.0 Radiation Therapy**
- 7.0 Patient Assessments**
- 8.0 Statistical Consideration**

- References**

Schema

Registration → 50 Gy in 25 daily fractions with proton radiotherapy → Surgery within 8 weeks after completion of radiation

Patient Population / disease: Histologically confirmed primary soft tissue sarcoma of the extremity and body wall; sarcomas of the retroperitoneum, hand, or foot are ineligible.

1.0 Introduction

1.1

Soft tissue sarcomas (STS) are relatively rare, heterogeneous malignancies that may arise almost anywhere in the body. However, the most common sites for STS are in the extremities and trunk. Kattan et al reported on 2136 patients treated at Memorial Sloan Kettering Cancer Center and observed these distributions: lower extremity (40.5%), upper extremity (16.6%) and thoracic or trunk (17.5%).¹ The mainstay of treatment for low-grade sarcomas is surgery with wide resection, which yields a high likelihood of local control; radical resection is required for high-grade lesions to achieve similar outcomes.²⁻³ The goal of surgery is to obtain a tumor-free margin; if that is not possible due to adjacent structures, adjuvant radiation is often employed.

Although delivery of radiotherapy in large or high-grade extremity sarcoma is considered standard, there is controversy regarding the appropriate timing of radiation delivery in relation to surgery. Nonetheless, data support preoperative radiotherapy as one of the standard options in the management of extremity STS. The advantages of preoperative (as opposed to postoperative) radiotherapy are that, generally, a lower dose and smaller radiation volumes may be used with potential improvement of long-term side effects and extremity function.⁴⁻⁶ Another potential advantage is assisting surgery through tumor shrinkage and reduction of tumor cell seeding.⁷⁻⁸ A retrospective review of 317 patients treated at the University of Florida from 1980-2007 with preoperative radiotherapy as part of a limb-conservation strategy showed that marginal resection (no tumor at inked margin) after preoperative radiation does not compromise local control or amputation-free survival when compared to wide/radical margins.⁹ This was felt to be related to radiosterilization of tumor cells within the reactive zone following preoperative radiation.

The disadvantage of preoperative radiation is the higher likelihood of postoperative wound complications.⁶⁻¹² A prospective randomized trial of preoperative versus postoperative radiotherapy by the NCIC CTG showed that the rate of wound complications increased from 17% to 35% with preoperative radiation therapy,⁶ albeit these complications were generally temporary, without significant effect on long-term function. Additionally, the NCIC trial showed that more serious chronic side effects occurred in the cohort receiving postoperative radiotherapy because those patients were generally treated to higher doses with larger treatment volumes.¹³

Combined conservative surgery and radiotherapy has been shown to achieve excellent local control in sarcoma patients following margin-negative surgery, but late radiation morbidity and reduced quality of life may result from adjuvant radiation.¹³⁻¹⁵ In the NCIC CTG trial, patients that received postoperative radiation had higher rates of grade 2 or greater fibrosis (48% versus 31.5%), increased edema (23% versus 15.1%) and joint stiffness (23% versus 17.8%).¹³ Although patients in the preoperative group had a lower rate of late effects, these effects were still substantial, occurring in 64.4% in the preoperative arm at 2 years following treatment. Increased field size and higher radiation dose were predictive of increased late effects. A prospective trial of sarcoma patients at Memorial Sloan Kettering Cancer Center, which randomized patients to postoperative adjuvant brachytherapy versus observation, showed a significant improvement in local control for patients receiving brachytherapy.⁷ The brachytherapy target region was determined by adding 2 cm margins in the superior and inferior dimensions of the tumor bed, with 1.5-2 cm

added in the medial and lateral directions. Among those patients with a local recurrence after adjuvant brachytherapy, the majority had “in-field” local recurrences. A retrospective review of patients treated in prospective trials at Princess Margaret Hospital, Toronto, Canada, for extremity soft tissue sarcoma with preoperative radiotherapy excised with a positive margin (including patients treated in the NCIC CTG trial) showed that including the postoperative radiation boost for patients treated with preoperative radiation and margin-positive excision did not provide an advantage in preventing local recurrence for patients treated with external-beam radiotherapy.¹⁶ Given that higher radiation doses also place patients at higher risk for late radiation morbidity, patients on the proposed trial will not undergo an additional postoperative radiation boost after adequate preoperative proton radiation.

More recently the Radiation Therapy Oncology Group (RTOG) has completed a phase II trial to determine whether a reduced radiation volume preoperatively with image-guided, intensity-modulated radiation therapy (IMRT) can improve upon late effects of lymphedema, subcutaneous fibrosis, and joint stiffness. This study will provide important information about whether late radiation morbidity is further reduced without compromising tumor control using reduced-field-volume preoperative radiotherapy. Preliminary results presented in an abstract at the 53rd annual meeting of the American Society for Radiation Oncology in October 2011 showed that acute toxicity profiles in patients with extremity STS treated with preoperative image-guided radiation therapy followed by surgery were acceptable, with 37% of patients experiencing major acute wound complications.¹⁶ Longer follow-up is required to show improvement in late toxicity and/or possible reduction in local control with smaller volumes irradiated.

The rationale for using proton beam radiotherapy is the superior dose distribution that can be achieved in comparison with photon-based techniques. Protons and other charged particles deposit little energy in tissue until near the end of the proton range; there, the residual energy is lost over a short distance, resulting in a steep rise in the absorbed dose known as the Bragg peak. Proton dose distributions are characterized by a lower-dose region in normal tissue proximal to tumor, a uniform high-dose region in the tumor, and zero dose beyond the tumor.¹⁸⁻²⁰ Also, IMRT treatment plans often include localized areas within the high-dose volumes where dose inhomogeneity can be as high as 15-20% above the target dose. Depending on the location of these “hot spots,” there can be unanticipated acute normal-tissue toxicity.²¹ Whether there are late effects attributable to these focal hot spots is unclear. Proton dose distributions are generally more homogenous. The dosimetric advantage of proton radiotherapy may translate into improved acute and late effects due to improved normal-tissue sparing in the treatment of extremity and truncal soft tissue sarcoma. However, these potential advantages need to be validated in clinical trials.

We propose a phase II study to evaluate the effect of preoperative proton radiotherapy on the reduction of late radiation morbidity, patterns of failure, local failure rate, and impact of late radiation morbidity on general quality of life (QOL).

2.0 Objectives

2.1 Primary objective

2.1.1 – To determine the effect of reduced radiation volume with proton radiotherapy on combined late radiation toxicities (>grade 2 lymphedema, subcutaneous fibrosis, and joint stiffness) at 2 years from the start of radiation treatment

2.2 Secondary Objectives

2.2.1 – To estimate CTCAE, v4.0 grade 3-5 adverse events;

2.2.2 – To determine patterns of failure, including local failure (in-field, marginal, out-of-field), regional failure, distant failure, and death without disease progression;

2.2.3 – To estimate the rates of local failure, local-regional failure, distant failure, distant-disease-free survival, disease-free survival, overall survival, and second primary tumor;

2.2.4 – To estimate rates of wound complications

2.2.5 – To correlate degree of late radiation morbidity at 2 years with quality of life assessment (FACT-G)

2.2.6 – To estimate the tumor necrosis rate following preoperative proton therapy

3.0 Patient Selection

3.1 Conditions for Patient Eligibility

3.1.1 – Histologically proven primary soft tissue sarcoma of the upper extremity (including shoulder), lower extremity (including hip) or body trunk (excluding retroperitoneum). Sarcomas of the hand or foot are ineligible.

3.1.2 – A biopsy must be done within 16 weeks prior to registration.

3.1.3 – No distant metastatic disease based on history/physical, MRI or CT of the tumor with contrast, CT scan of chest, and CT scan of abdomen and pelvis for intermediate to high-grade lesions. These scans must be done within 16 weeks prior to registration.

3.1.4 – Evaluation by surgeon, with documentation that the tumor is resectable

3.1.5 – ECOG performance status 0-1

3.1.6 – Age >18

2.0 Objectives

2.1 Primary objective

2.1.1 – To determine the effect of reduced radiation volume with proton radiotherapy on combined late radiation toxicities (>grade 2 lymphedema, subcutaneous fibrosis, and joint stiffness) at 2 years from the start of radiation treatment

2.2 Secondary Objectives

2.2.1 – To estimate CTCAE, v4.0 grade 3-5 adverse events;

2.2.2 – To determine patterns of failure, including local failure (in-field, marginal, out-of-field), regional failure, distant failure, and death without disease progression;

2.2.3 – To estimate the rates of local failure, local-regional failure, distant failure, distant-disease-free survival, disease-free survival, overall survival, and second primary tumor;

2.2.4 – To estimate rates of wound complications

2.2.5 – To correlate degree of late radiation morbidity at 2 years with quality of life assessment (FACT-G)

2.2.6 – To estimate the tumor necrosis rate following preoperative proton therapy

3.0 Patient Selection

3.1 Conditions for Patient Eligibility

3.1.1 – Histologically proven primary soft tissue sarcoma of the upper extremity (including shoulder), lower extremity (including hip) or body trunk (excluding retroperitoneum). Sarcomas of the hand or foot are ineligible.

3.1.2 – A biopsy must be done within 16 weeks prior to registration.

3.1.3 – No distant metastatic disease based on history/physical, MRI or CT of the tumor with contrast, CT scan of chest, and CT scan of abdomen and pelvis for intermediate to high-grade lesions. These scans must be done within 16 weeks prior to registration.

3.1.4 – Evaluation by surgeon, with documentation that the tumor is resectable

3.1.5 – ECOG performance status 0-1

3.1.6 – Age >18

3.1.7 – For females of childbearing potential, a serum pregnancy test within 4 weeks prior to registration

3.1.8 – Patient must practice adequate contraception

3.1.9 – Patient must provide study-specific informed consent prior to study entry

3.1.10 – CBC/differential obtained within 12 weeks prior to registration with adequate bone marrow function (ANC >1500 cells/mm³, platelets >100,000, and Hemoglobin >8 g/dl.

3.2 Conditions for Patient Ineligibility

3.2.1 – Patients with sarcoma of the head, neck, intra-abdominal or retroperitoneal region, hand, or foot

3.2.2 – Histopathology demonstrating rhabdomyosarcoma, extraosseous primitive neuroectodermal tumor (PNET), soft tissue Ewing's sarcoma, osteosarcoma, Kaposi's sarcoma, angiosarcoma, aggressive fibromatosis, dermatofibrosarcoma protuberans or chondrosarcoma

3.2.3 – Lymph node or distant metastases

3.2.4 – Prior invasive malignancy (except non-melanomatous skin cancer) unless disease free for a minimum of 3 years

3.2.5 – Prior radiotherapy to the potential target anatomic region that would result in overlap of radiation fields for current sarcoma

3.2.6 – Pregnancy or women of childbearing potential and men who are sexually active and not willing/able to used medically acceptable forms of contraception;

4.0 Drug Therapy – No Drugs used in this study

5.0 Surgery

5.1 Initial Biopsy

5.1.1 – An incisional biopsy or core needle biopsy is required. If needle biopsy is done, the site should be tattooed for future identification. Biopsy should be performed in such a way as to permit excision of the biopsy site at the time of formal resection

5.2 Surgery

5.2.1 –The surgeon and radiation oncologist must see the patient prior to preoperative therapy.

5.2.2 –Margin status. Sarcomas require resection of the entire tumor as well as a margin of normal tissue.²² A positive margin or a negative margin of 2 mm or less has been shown to have a higher risk of local recurrence and decreased long-term survival.²³ The goal of radiation is to “sterilize” the periphery of the tumor to kill or disable tumor cells most at risk of remaining in the wound. In areas with ample soft tissue that can be removed without compromising future function or wound closure, wide margins is the goal of treatment; associated rates of local failure are low in such instances. Margins will be determined by the surgeon; the goal is to achieve at least a 2 mm negative margin resection. The surgeon should determine and document a high possibility of limb preservation approach after preoperative radiation to obtain local control.

However, smaller margins can be acceptable if it allows for limb-sparing surgery with conserved functional outcomes. A retrospective review of 132 patients treated at Massachusetts General Hospital from 1974-1998 for extremity STS with preoperative RT and limb-sparing surgery showed that 5-year local control was inferior in patients with positive margins (82%) compared to negative margins \leq 1 mm (94%) and $>$ 1 mm (97%).²⁴ A modern series from Massachusetts General Hospital of 56 similarly treated patients reported a 5-year local control rate of 93.2%, with all local failures observed occurring in patients with positive margins or $<$ 1 mm margins.²⁵ Similarly treated patients at MD Anderson Cancer Center showed decreased local control (62% vs 91%) for positive surgical margins compared to negative margins.²⁶ When radiation is used, margins that are 1 mm or less can be accepted, allowing for limb-sparing surgery and decreased morbidity.

Additionally, when the tumor grows close to a critical structure such as a major motor nerve or bone, the margins will be unavoidably close for function preservation. Careful dissection of these fixed structures, such as epineural dissection of a major nerve or periosteal resection along bone, is possible when combined with adjuvant radiation therapy.^{27,28} These “planned positive” margins have similar local recurrence rates to those observed with negative margins.²⁹ After radiation, every effort should be made to have limb preservation surgery unless there is documented evidence of tumor progression during or after the course of radiation that would require amputation for an appropriate margin resection.

6.0 Radiation Therapy

6.1 Dose Specification

6.1.1 – Preoperative proton radiation therapy. The total dose will be 50 Gy in 25 fractions, with a minimum of 90% of PTV receiving 50 Gy.

6.2 Technical factors

6.2.1 -Treatment will be delivered with selection of appropriate proton energies to optimize the radiotherapy dose distribution within the target volume and minimize dose to non-target tissues

6.2.2 – PTV includes setup uncertainty and lateral uncertainties perpendicular to the beam direction. Each beam will be optimized to adjust for range uncertainties to guarantee adequate coverage of the PTV.

6.3 Localization, Simulation, and Immobilization

6.3.1 – Patient positioning will be based on clinical judgment to best achieve the ideal dose distribution using a variety of devices for limb/body immobilization

6.4 Treatment planning/Volume definitions

6.4.1 – CT-based 3D treatment planning will be used for all patients. Simulation will be done on a CT scan with limb/body immobilization

6.4.2 – Gross Tumor Volume (GTV): Gross tumor will be defined as MRI T1 plus contrast image (MRI with contrast is required). Fusion of MRI and CT will be used to delineate the GTV for radiotherapy planning.

6.4.3 – Clinical Target Volume (CTV): Include gross tumor and clinical microscopic margins. Typically CTV = GTV and suspicious edema (defined by MRI T2 images) plus 2 cm margins in the longitudinal directions. If this causes the radiation field to extend beyond the compartment, the field can be shortened to include the end of the compartment. The radial margin from the lesion should be 1 cm, including any portion of the tumor not confined by an intact fascial barrier or bone or skin surface.

6.4.4 – Planning Target Volume (PTV): Includes CTV and error of setup and organ motion. The PTV will include setup uncertainties, depending on immobilization method and daily image guidance.

6.4.5 – Skin surfaces should not be contoured in CTV or PTV unless these are involved by gross tumor. If the incisional biopsy scar is small and will be resected at the time of surgery, it may or may not be contoured as CTV.

6.5 Critical Structures

6.5.1 – Radiation dose to normal tissues should be kept within accepted normal tissue tolerances when using standard 2 Gy fractionation schedules. Every effort will be made to avoid treating the full circumference of an extremity; avoid treating the anus, vulva, scrotum, or lung; and avoid treating the skin to the full dose over areas commonly traumatized (e.g. elbow, knee, etc.), and femoral head/neck.

6.5.2 – If tumor is close to the structures mentioned in 6.5.1, typically less than 50% volume of the anus and vulva should receive 30 Gy; less than 50% volume of the testis should receive 3 Gy, if fertility preservation is desired; 20% of lung should receive less than 20 Gy (V20); and less than 5% of the femoral head/neck should receive 60 Gy. Less than 50% of any joints (including shoulder, elbow, and knee) should receive 50 Gy. Less than 50% of kidney volumes should receive 14 Gy. For any other normal-tissue structures, no radiation dose more than established TD 5/5 limits should be given.

6.5.3 – No more than 50% of a longitudinal strip of skin and subcutaneous tissue of an extremity should receive 20 Gy. This strip of normal tissue will be contoured by the treating radiation oncologist. Full prescription dose to skin over areas commonly traumatized should be avoided.

6.5.4 – No more than 50% of weight-bearing bone within the radiation field should receive 50 Gy, except when the tumor invades the bone or when there is circumferential involvement of the tumor in more than a quarter of the bone, or when the bone will be resected in a subsequent surgical resection after radiation.

6.5.5 – There is no special requirement for skin dose limit. However, skin sparing is recommended if possible. Skin surface (5 mm thickness) including scar for incision biopsy is not included in CTV or PTV and is not bolused, unless the biopsy scar is not subsequently resected after preoperative radiotherapy.

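### The only numeric lung limit (section 6.5.2) puts its inequality on the dose instead of the volume, so read literally it is not a V20 cap (minor)

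*Combined protocol and SAP*

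**What the plan says.** Section 6.5.2 lists dose-volume limits for use when the tumour lies near one of the structures named in section 6.5.1. It opens with "If tumor is close to the structures mentioned in 6.5.1, typically less than 50% volume of the anus and vulva should receive 30 Gy". Later in the same sentence the lung limit reads "20% of lung should receive less than 20 Gy (V20" (the bracket then closes), and the next limit is "less than 5% of the femoral head/neck should receive 60 Gy". The same item goes on to joints and to kidney: "Less than 50% of kidney volumes should receive 14 Gy". Section 6.5.3 limits a strip of skin and subcutaneous tissue. Section 6.5.4 limits bone: "No more than 50% of weight-bearing bone within the radiation field should receive 50 Gy".

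The other text bearing on lung has no number. Section 6.5.1 says "Radiation dose to normal tissues should be kept within accepted normal tissue tolerances" and asks for every effort to "avoid treating the anus, vulva, scrotum, or lung". Section 6.2.1 asks that proton energies be chosen to "optimize the radiotherapy dose distribution within the target volume and minimize dose to non-target tissues". The TD 5/5 sentence that closes the list in section 6.5.2 applies to structures not already named, so by its wording it does not reach lung.

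**The concern.** A V20 limit normally caps the share of lung that receives 20 Gy or more. This clause instead names a share of lung that should stay below 20 Gy. It therefore describes a minimum amount of spared lung and contradicts its own V20 label. A plan can satisfy the sentence while exceeding the evident limit several times over.

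The clause matters only where lung lies near the field. Section 3.1.1 admits body-trunk tumours, and it admits shoulder tumours under the upper extremity. The prescription in section 6.1.1 is 50 Gy in 25 fractions, so nearby lung can receive more than 20 Gy. At stake is whether the protocol's one numeric lung check separates acceptable plans from unacceptable ones. No statistical quantity depends on it.

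**Working it through.** The plan reports no figure to reproduce here. The check is a comparison of wording followed by one line of arithmetic.

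**Step 1: compare the limits.** There are eight percentage limits: six in section 6.5.2, one in 6.5.3 and one in 6.5.4.

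| Section | Structure | Volume term | Dose term | Inequality falls on |
|---|---|---|---|---|
| 6.5.2 | Anus, vulva | < 50% | 30 Gy | volume |
| 6.5.2 | Testis (if fertility is to be preserved) | < 50% | 3 Gy | volume |
| 6.5.2 | **Lung** | **20%** | **< 20 Gy** | **dose** |
| 6.5.2 | Femoral head/neck | < 5% | 60 Gy | volume |
| 6.5.2 | Joints | < 50% | 50 Gy | volume |
| 6.5.2 | Kidney | < 50% | 14 Gy | volume |
| 6.5.3 | Skin and subcutaneous strip | ≤ 50% | 20 Gy | volume |
| 6.5.4 | Weight-bearing bone | ≤ 50% | 50 Gy | volume |

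Seven of the eight cap the volume. Lung is the exception, in the same sentence as three limits worded the usual way. A symbol lost in PDF conversion is not a persuasive explanation, because the inequality is written out in words and attached to the dose.

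**Step 2: convert both readings to V20.** Assumption: V20 has its usual meaning, the percentage of lung receiving at least 20 Gy. Then

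share of lung below 20 Gy = 100% − V20.

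- Literal wording, read as at least 20% of lung below 20 Gy: 100% − V20 ≥ 20%, so V20 ≤ 80%.
- Literal wording, read as exactly 20%: V20 = 100% − 20% = 80%.
- Evident intention, following the label and the seven neighbouring limits: V20 < 20%.

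Neither literal reading gives an upper limit of 20%. The literal ceiling is 80 / 20 = 4 times the evident one.

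**Step 3: apply both rules to example plans**, using the at-least reading.

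| V20 | Lung below 20 Gy | Literal clause | Evident intention |
|---|---|---|---|
| 10% | 90% | met | met |
| 50% | 50% | met | not met |
| 75% | 25% | met | not met |
| 85% | 15% | not met | not met |

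The rules disagree from V20 = 20% to V20 = 80%, a band of 80 − 20 = 60 percentage points.

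**Step 4: look for a number elsewhere.** There is none. Sections 6.5.1 and 6.2.1 still apply to plans inside the band, but only qualitatively.

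**The case against.** The strongest reply is that a competent planner would not be misled. The clause contains the name of the metric, the 20% and the 20 Gy, and it sits among limits that point to the right reading. The 60-point band appears only if the V20 label is ignored, an at-least is supplied before the 20%, and the clause is read apart from sections 6.5.1 and 6.2.1. A plan putting most of the lung at 20 Gy or more would be hard to square with those sections. The limits in section 6.5.2 are also qualified as typical and apply only to nearby tumours, so they read as guidance. The document ties no plan approval or deviation scoring to them; the compliance reporting in section 8.3.1.3 concerns the protocol prescription. Finally, the primary endpoint is lymphedema, fibrosis and joint stiffness, not lung toxicity.

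Most of this stands, and it is why the point is minor. The intended limit can be inferred, the band describes the literal text alone, and the general rules still restrain lung dose. The inversion itself remains. A reader recovers the limit only by setting aside what the sentence says, and no correctly worded lung number exists elsewhere to fall back on.

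**Conclusion.** The concern holds as a minor wording error in an operative treatment-planning limit. Its size can be stated only in terms of the text: a literal ceiling of V20 = 80% against an evident ceiling just under 20%, with opposite answers for V20 from 20% to 80%. How many patients this concerns cannot be derived, because the document does not say how many tumours will lie near lung.

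The conclusion rests on two assumptions: that V20 carries its usual meaning, and that 20% is the intended volume figure. The second is inferred from the label and the neighbouring limits and needs confirmation. The finding questions neither the threshold nor any design decision, and section 6.5.2 does not conflict with the aim in 6.5.1 of avoiding lung, since it covers cases where the tumour is close.

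**What to change.** Move the inequality from the dose to the volume. Suggested wording for the clause in section 6.5.2: *less than 20% of lung should receive 20 Gy or more (V20 < 20%)*. The radiation oncology lead should confirm the 20% figure and state whether it refers to one lung or both, which the present text leaves open.

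The cost is a one-clause wording amendment, with no added procedures, patients or analyses.
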